2.1. Purpose of the Analyses

These analyses will assess the efficacy of ciprofloxacin for treatment of uncomplicated *Neisseria gonorrhoeae* infections with *gyrA* serine 91 genotype and will be included in the clinical study report.

3. STUDY OBJECTIVES AND ENDPOINTS

3.1. Study Objectives

3.1.1. Primary Objectives

1. To determine the efficacy of ciprofloxacin for treatment of uncomplicated *Neisseria gonorrhoeae* infections with *gyrA* serine 91 genotype.

3.1.2. Secondary Objectives

1. To investigate efficacy of ciprofloxacin for treatment of uncomplicated *gyrA* serine 91 genotype *Neisseria gonorrhoeae* infection by anatomic site.
2. To determine the sensitivity of the *gyrA* assay for detection of ciprofloxacin-susceptible *Neisseria gonorrhoeae* infections.

3.1.3. Exploratory Objectives

1. To characterize *N. gonorrhoeae* isolates and non-*gyrA* gene-dependent mechanisms of ciprofloxacin resistance post-treatment of uncomplicated *N. gonorrhoeae* infection by anatomic site using traditional and molecular methods like genotyping and sequencing.
2. To investigate the efficacy of ciprofloxacin for treatment of uncomplicated serine 91 *gyrA* *N. gonorrhoeae* infections by demographic and clinical characteristics.

3.2. Endpoints

3.2.1. Primary Outcome Measure

1. The proportion of subjects infected with *gyrA* serine 91 genotype *N. gonorrhoeae* with microbiological cure at Visit 2 (Day 5-10)

3.2.2. Secondary Outcome Measure

1. The proportion of subjects infected with *gyrA* serine 91 genotype *N. gonorrhoeae* with microbiological cure at each anatomic site (throat, rectum, male or female urogenital tract) at Visit 2 (Day 5-10)
2. The proportion of subjects infected with *gyrA* serine 91 genotype *N. gonorrhoeae* identified by *gyrA* gene PCR who have ciprofloxacin-susceptible *N. gonorrhoeae* as identified by culture-based antimicrobial susceptibility testing at Visit 1 (Day 1)

3.2.3. Exploratory Outcome Measures

1. Identification and characterization of non-*gyrA* gene-dependent mechanisms of ciprofloxacin resistance by genotyping and whole genome sequencing (e.g., Illumina) of nucleic acid isolated from uncured subjects at Visit 2 (Day 5-10). Genotyping and sequencing may be performed on nucleic acid isolated from different anatomic sites.
2. The proportion of subjects infected with *gyrA* serine 91 genotype *N. gonorrhoeae* with microbiological cure at Visit 2 (Day 5-10) by demographic and clinical characteristics.

3.3. Study Definitions and Derived Variables

3.3.1. Baseline untreated serine 91 *gyrA* genotype *N. gonorrhoeae* Diagnosis

For a particular anatomical site, a subject who has not been treated for *N. gonorrhoeae* prior to enrollment into the study will be identified as having untreated serine 91 *gyrA* *N. gonorrhoeae* if there is:

- Detectable *N. gonorrhoeae* at Visit 1 via culture, i.e. positive *N. gonorrhoeae* culture from the swab taken at Visit 1, and
- Detection of wild type *gyrA* by the real-time PCR analysis of the *gyrA* gene from the swab taken at Visit 1.

3.3.2. Microbiological Outcome Status

- 1 Microbiological outcome status for the primary analysis is evaluated at Visit 2 and is defined as follows:
 - Microbiological Cure: *N. gonorrhoeae* not detectable by culture from all anatomical sites that had detectable *N. gonorrhoeae* at Visit 1.
 - Microbiological Failure: *N. gonorrhoeae* detectable by culture from at least one anatomical site that had detectable *N. gonorrhoeae* at Visit 1.
 - Non-evaluable: At least one of the following:
 - Subject did not return for Visit 2, or
 - Culture results at Visit 2 were not available for any reason, or
 - Subject could not be evaluated for microbiological outcome status for any other reason.
- 2 For the analysis of secondary objective 1, microbiological outcome status at each anatomical site is evaluated at Visit 2 and is defined for a particular anatomical site as follows:
 - Microbiological Cure: *N. gonorrhoeae* not detectable by culture at the particular anatomical site that had detectable *N. gonorrhoeae* at Visit 1.
 - Microbiological Failure: *N. gonorrhoeae* detectable by culture at the particular anatomical site that had detectable *N. gonorrhoeae* at Visit 1.
 - Non-evaluable: At least one of the following:
 - Subject did not return for Visit 2, or
 - Culture results at Visit 2 were not available for any reason, or
 - Subject could not be evaluated for microbiological outcome status for any other reason.

3.3.3. Sensitivity of the *gyrA* assay

For the analysis of the sensitivity of the *gyrA* assay for the detection of ciprofloxacin-susceptible *N. gonorrhoeae* infections (secondary objective 2), two measures will be estimated. First, the sensitivity of the assay will be estimated using the following (overall and separately for each anatomical site):

True Positives (TP): the number wild type *gyrA* infections that are ciprofloxacin-susceptible *N. gonorrhoeae* as identified by culture-based antimicrobial susceptibility testing at Visit 1.

False Negatives (FN): the number of non-wild type *gyrA* infections that are ciprofloxacin-susceptible *N. gonorrhoeae* as identified by culture-based antimicrobial susceptibility testing at Visit 1.

$$\text{Sensitivity} = \text{TP} / (\text{TP} + \text{FN})$$

Given the design of the study, the estimate of sensitivity may be biased because subjects with no wild type infections are not enrolled and thus their samples are not tested for culture-based susceptibility testing. To supplement the estimates of sensitivity, the assay's positive predictive value (PPV) will also be estimated. PPV is calculated using the following (overall and separately for each anatomical site):

True Positives (TP): the number wild type *gyrA* infections that are ciprofloxacin-susceptible *N. gonorrhoeae* as identified by culture-based antimicrobial susceptibility testing at Visit 1.

False Positives (FP): the number of wild type *gyrA* infections that are not ciprofloxacin-susceptible *N. gonorrhoeae* as identified by culture-based antimicrobial susceptibility testing at Visit 1.

$$\text{PPV} = \text{TP} / (\text{TP} + \text{FP}).$$

3.3.4. Baseline Value

The baseline value for all variables will be defined as the last value obtained prior to the dose of ciprofloxacin.

3.3.5. Within Window Test of Cure Visit

Version 6.0 of the protocol (03 July 2018) was updated to expand the visit window for Visit 2 from Day 5-9 to Day 5-10. For subjects enrolled under version 6.0 (or later) of the protocol, the Test of Cure visit will be considered within window if the visit occurred between Days 5 and 10 (inclusive). For subjects enrolled under a version prior to version 6.0, Test of Cure visit will be considered within window if the visit occurred between Days 5 and 9 (inclusive).

3.3.6. Treatment Compliance

A subject will be considered compliant with study treatment if the subject is able to swallow the pill and not vomit within 1 hour of administration. Otherwise, the subject will be considered non-compliant.

3.3.7. Symptomatic/Asymptomatic Status

For female subjects with baseline cervicovaginal infection, subjects will be classified as symptomatic if they report any of the following symptoms at baseline: abnormal vaginal discharge, abnormal vaginal bleeding, or pain during intercourse.

For male subjects with baseline urethral infection, subjects will be classified as symptomatic if they report any of the following symptoms at baseline: urethral discharge or pain with urination.

For subjects with baseline rectal infection, subjects will be classified as symptomatic if they report any of the following symptoms at baseline: anorectal pain, anorectal discharge, or anorectal bleeding.

For subjects with baseline pharyngeal infection, subjects will be classified as symptomatic if they report having a sore throat at baseline.

For all anatomic locations, baseline infections are those confirmed by culture. Subjects with baseline infections will be considered asymptomatic if they do not affirm these symptoms at baseline.

3.3.8. Ciprofloxacin Susceptible Infection

Ciprofloxacin susceptibility will be determined via culture-based antimicrobial susceptibility testing. An infection will be deemed susceptible to ciprofloxacin if the reported minimum inhibitory concentration for the isolate is < 1 mcg/ml.

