2.2 Rationale

Resistance to extended-spectrum cephalosporins was first identified in Japan and is increasing in the western United States and among men who have sex with men [11]. Antimicrobial resistance mechanisms have been fairly well described as mutations in target proteins, alterations in cell wall components, or increases in efflux pumps [2].

Currently, the nationwide frequency of *N. gonorrhoeae* isolates with decreased ciprofloxacin susceptibility, minimum inhibitory concentration (MIC) ≥ 0.125 $\mu\text{g/mL}$, or resistance (MIC ≥ 0.5 $\mu\text{g/mL}$) is relatively modest at 13.5% [12]. Prior experience with changing antibiotic treatment guidelines has demonstrated that major shifts in antibiotic use may modify the ecology of drug resistance. For example, restricting erythromycin use in Group A streptococcal infections in Finland led to a population-level decrease in erythromycin-resistance in that organism [13].

While molecular methods to diagnose *N. gonorrhoeae* have greatly improved the detection of infection [14], they have historically precluded the ability to perform antibiotic susceptibility testing. Although regional surveillance data critically inform treatment recommendations, those data cannot be used for real-time individualized clinical management. The clinical validation of an assay to determine the ciprofloxacin susceptibility of *N. gonorrhoeae* infections could result in increased use of ciprofloxacin for ciprofloxacin-susceptible *N. gonorrhoeae* infections and resultant decreased use of extended-spectrum cephalosporins, thereby reducing the selection pressure for cephalosporin resistance in *N. gonorrhoeae*. An immediate benefit to taking ciprofloxacin would be for those with cephalosporin allergies who would have to take combination therapy that is more difficult to administer.

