8.2.2 Special Assays or Procedures for Enrolled Subjects

Urine collected at Visit 1 will be analyzed for detecting pregnancies by use of a standard rapid urine β hCG assay.

Swabs (non-cotton) will be used to collect specimens at each site (throat, rectal, urethral or cervical) for *N. gonorrhoeae* culture. The swab will be immediately smeared onto a modified Thayer Martin plate, which is placed into a candle jar or other CO₂-rich transport media, at the clinic. These plates will be transported in the CO₂-rich transport media to the local laboratory for culture for *N. gonorrhoeae*. The local laboratory will culture and isolate the gonococcal strain, according to their SOP for *N. gonorrhoeae* culture. *N. gonorrhoeae* culture specimens will be obtained first; this sequence maximizes the load collected, which increases the likelihood of a successful culture. A second swab or urine will be collected for NAAT for *N. gonorrhoeae* detection, according to the

laboratory SOP, using a collection kit with liquid transport specific to the local protocols (e.g. unisex swab specimen collection kit).

For each positive culture (regardless of anatomical site or visit number), a subculture of each gonococcal isolate will be subject to antimicrobial susceptibility testing using the agar dilution method for azithromycin, cefixime, ceftriaxone, ciprofloxacin, gentamicin, penicillin, spectinomycin, and tetracycline. M100 Clinical and Laboratory Standards Institute (CLSI) interpretive criteria will be used to evaluate susceptibility to each agent, with the exception of azithromycin, where CDC criteria will be used [16].

For each positive NAAT, or negative NAAT with a positive culture for the same visit, up to two 500 µL aliquots of the specimen will be frozen in screw-top 2.0 mL tubes, at -70°C for discordant resolution, if needed. These frozen remnants will be stocked at the local laboratory until they are sent to the central laboratories approximately halfway through the study and at study completion.

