Intent-to-Treat (ITT) Population	Number of Infections with Microbiological Cures, n	x	x	x	x
	Number of Infections, N	x	x	x	x
	Microbiological Cure Rate, %	xx.x	xx.x	xx.x	xx.x
	95% CI, %	xx.x, 100	xx.x, 100	xx.x, 100	xx.x, 100
Microbiological Intent-to-Treat (micro-ITT) Population	Number of Infections with Microbiological Cure, n	x	x	x	x
	Number of Infections, N	x	x	x	x
	Microbiological Cure Rate, %	xx.x	xx.x	xx.x	xx.x
	95% CI, %	xx.x, 100	xx.x, 100	xx.x, 100	xx.x, 100
Per-Protocol (PP) Population	Number of Infections with Microbiological Cure, n	x	x	x	x
	Number of Infections, N	x	x	x	x
	Microbiological Cure Rate, %	xx.x	xx.x	xx.x	xx.x
	95% CI, %	xx.x, 100	xx.x, 100	xx.x, 100	xx.x, 100

Implementation Notes: The ITT Population, Micro-ITT Population and PP Population will be based on the anatomical site.

Table 12: Summary of *gyrA* Assay Results and Culture-Based Antimicrobial Susceptibility Testing at Visit 1—ITT population

	Anatomic Site		Culture-Based Antimicrobial Susceptibility Testing					
			Susceptible		Not Susceptible		Total	
			n	%	n	%	n	%
gyrA Assay	All Sites	Wild Type gyrA detected	xx	xx	xx	xx	xx	xx
		Mutant gyrA detected	xx	xx	xx	xx	xx	xx
		Total	xx	xx	xx	xx	xx	100
	Urethral	Wild Type gyrA detected	xx	xx	xx	xx	xx	xx
		Mutant gyrA detected	xx	xx	xx	xx	xx	xx
		Total	xx	xx	xx	xx	xx	100
	Cervical	Wild Type gyrA detected	xx	xx	xx	xx	xx	xx
		Mutant gyrA detected	xx	xx	xx	xx	xx	xx
		Total	xx	xx	xx	xx	xx	100
	Rectal	Wild Type gyrA detected	xx	xx	xx	xx	xx	xx
		Mutant gyrA detected	xx	xx	xx	xx	xx	xx
		Total	xx	xx	xx	xx	xx	100
	Pharyngeal	Wild Type gyrA detected	xx	xx	xx	xx	xx	xx
		Mutant gyrA detected	xx	xx	xx	xx	xx	xx
		Total	xx	xx	xx	xx	xx	100

The denominator for percentages is based on the number of instances in which swabs taken from a subject at Visit 1 resulted in a determinate *gyrA* Assay result and a determinate culture-based antimicrobial susceptibility test result. If either *gyrA* Assay result or culture-based antimicrobial susceptibility test result is indeterminate or missing, both results will be excluded. Susceptible is defined as an MIC of < 1 ug/ml as reported by the antimicrobial susceptibility testing.

Implementation Notes: The ITT Population will be based on the anatomical site.

Table 13: Culture Results by Time Point and Anatomical Sites

Time Point	Result	Urethral (N=X)		Cervical (N=X)		Rectal (N=X)		Pharyngeal (N=X)	
		n	%	n	%	n	%	n	%

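### The SAP counts ciprofloxacin MIC below 1 mcg/ml as susceptible without a source; this conflicts with protocol 2.2, is not tied to the M100 criteria in protocol 8.2.2, and can only favour PPV

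*SAP*

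**What the plan says.** SAP 3.3.8 defines the culture-based reference result: "An infection will be deemed susceptible to ciprofloxacin if the reported minimum inhibitory concentration for the isolate is < 1 mcg/ml". The footnote to SAP Table 12 repeats it: "Susceptible is defined as an MIC of < 1 ug/ml as reported by the antimicrobial susceptibility testing". Neither place cites a standard or gives a reason for the value 1.

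SAP 3.3.3 builds secondary objective 2 on this definition. True positives are wild-type gyrA infections that are susceptible, false positives are wild-type infections that are not susceptible, and false negatives are non-wild-type infections that are susceptible. Sensitivity is TP/(TP+FN) and PPV is TP/(TP+FP). Secondary outcome measure 2 (section 3.2.2 in both documents) is the share of subjects with a serine 91 genotype whose isolate is susceptible by culture. In form, that is a PPV.

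The protocol speaks to susceptibility in two places. Section 2.2 gives a national frequency of "isolates with decreased ciprofloxacin susceptibility, minimum inhibitory concentration (MIC) ≥ 0.125" µg/mL, "or resistance (MIC ≥ 0.5" µg/mL). Section 8.2.2 gives the operative laboratory rule: "M100 Clinical and Laboratory Standards Institute (CLSI) interpretive criteria will be used to evaluate susceptibility to each agent", with an exception for azithromycin only. It states no ciprofloxacin breakpoint. SAP section 15 reports no changes to the planned analyses.

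**The concern.** The documents classify the same isolate differently. At MIC 0.5 to below 1 it is resistant in protocol 2.2 and susceptible in SAP 3.3.8. At 0.125 to below 0.5 it has decreased susceptibility in the protocol and is plainly susceptible in the SAP. A reader cannot tell whether below 1 is meant to implement the M100 criteria or to replace them.

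The choice matters because it fixes TP, FP and FN for secondary objective 2. A wild-type call on an isolate with a raised MIC is a discordance between genotype and culture, and the protocol takes an interest in such cases: exploratory objective 1 concerns resistance not explained by gyrA, and section 8.2.2 sends isolates for sequencing when culture shows resistance and gyrA predicts susceptibility. Under the SAP cut-off, any such isolate below 1 enters Table 12 as an assay success. Table 12 and Listing 5 show only susceptible or not susceptible, so neither reveals how many isolates owe their status to the cut-off.

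**Working it through.** **Definitions side by side**

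| MIC (mcg/ml) | Protocol 2.2 | SAP 3.3.8 and Table 12 |
|---|---|---|
| below 0.125 | neither category | susceptible |
| 0.125 to below 0.5 | decreased susceptibility | susceptible |
| 0.5 to below 1 | resistance | susceptible |
| 1 or more | resistance | not susceptible |

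The M100 criteria of protocol 8.2.2 cannot be added as a column, because the documents do not state their numbers.

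**Expected denominator.** The plan gives no PPV or sensitivity figure to reproduce. Its enrolment figure does reproduce: with 25% culture negative and 10% excluded (protocol 11.2), 257/(0.75 × 0.90) = 380.7, rounded up to 381. Expected culture-positive subjects are 381 × 0.75 = 285.75, about 286. I use N = 286 wild-type isolates with both results determinate, which is an assumption. SAP 8.2 runs this analysis in the ITT population, and SAP 6.5 and Table 12 restrict it to specimens with both results determinate. Subjects infected at several sites would raise N; missing or mutant results would lower it.

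**PPV.** Let k be the number of wild-type isolates between a lower cut-off (0.125 or 0.5) and 1. Moving the cut-off up to 1 turns k false positives into true positives, while TP+FP stays at N. The change is exactly k/N and cannot be negative. The documents give no MIC distribution, so k is assumed. The middle column below also assumes no wild-type isolate at 1 or more; the size of the change does not depend on that.

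| k | PPV at lower cut-off | PPV at below 1 | Change (points) |
|---|---|---|---|
| 2 | 284/286 = 99.3% | 100% | 0.7 |
| 5 | 281/286 = 98.3% | 100% | 1.7 |
| 10 | 276/286 = 96.5% | 100% | 3.5 |
| 14 | 272/286 = 95.1% | 100% | 4.9 |

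For k = 14, a one-sided 95% modified Jeffreys lower bound would be 92.7% at the lower cut-off and 0.05^(1/286) = 99.0% at below 1. As an outer illustration, applying the whole 13.5% of protocol 2.2 gives k = 39 and 39/286 = 13.6 points. That is not an estimate: the 13.5% describes all national isolates, not wild-type ones, and its categories have no upper limit at 1.

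**Sensitivity.** Let a = 286 − k be the wild-type isolates below the lower cut-off, c the mutant isolates below it, and m the mutant isolates in the gap. Sensitivity is a/(a+c) at the lower cut-off and (a+k)/(a+k+c+m) at below 1. It rises only if k/(k+m) exceeds the first value.

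| k, m, c | Lower cut-off | Below 1 |
|---|---|---|
| 6, 0, 3 | 280/283 = 98.94% | 286/289 = 98.96% |
| 14, 0, 3 | 272/275 = 98.91% | 286/289 = 98.96% |
| 6, 3, 0 | 280/280 = 100% | 286/289 = 98.96% |
| 14, 14, 3 | 272/275 = 98.91% | 286/303 = 94.39% |

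The gain is at most 0.05 points in the cases without mutant isolates in the gap. With them, sensitivity falls by 1.0 and 4.5 points.

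**The case against.** The sponsor has several good answers.

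- **The protocol 2.2 values are background.** They describe national surveillance in the rationale and are not the trial's analysis definition. That stands. The operative rule is M100, and these documents cannot show whether below 1 matches it. This shifts the burden without removing it, because the SAP neither cites M100 at 3.3.8 nor explains the number.
- **The gap isolates are not hidden.** SAP 8.2.1 plans ciprofloxacin MIC50, MIC90 and range (Tables 16 and 17) and MIC histograms in the micro-ITT and PP populations, both of which require wild-type gyrA. Wild-type isolates between 0.125 and 1 would largely be visible there. This is true, but those outputs do not recompute PPV and they use populations other than the ITT population of Table 12.
- **Little rests on it.** The primary endpoint depends on genotype and culture cure (SAP 3.3.2 and 8.1), not on MIC. No success threshold is set for PPV or sensitivity, and SAP 3.3.3 already warns that sensitivity may be biased by the enrolment rule. This also stands and limits the weight of the point.

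A reader might go further and infer that assay accuracy as a whole is inflated. The documents do not support that. Sensitivity, the measure named in secondary objective 2, can fall under the SAP rule, and PPV rises only if wild-type isolates actually lie in the gap. Nor do they support inferring that an intermediate M100 category has been folded into susceptible: they state no M100 breakpoints and name no intermediate category for ciprofloxacin.

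**Conclusion.** The inconsistency is real and unexplained. MIC 0.5 to below 1 is resistant in protocol 2.2 and susceptible in SAP 3.3.8, the link to the M100 commitment in protocol 8.2.2 is missing, and no change is declared. Relative to a cut-off at 0.125 or 0.5, the SAP rule can only raise PPV or leave it unchanged, by k/N.

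The size is conditional. It is 0.7 to 3.5 points for 2 to 10 wild-type gap isolates among an assumed 286, and zero if there are none. Scaling to the per-protocol target of 257 would give slightly larger figures (0.8 to 3.9 points for the same counts), but that is not the population in which the SAP runs this analysis. The direction for sensitivity is undetermined. The primary test, sample size and futility rule do not use this cut-off.

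Confidence is high for the mismatch and for the direction of the PPV effect. It is not high for the amount, which rests on assumed counts. The point should be settled before database lock because it defines a secondary outcome.

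**What to change.** 1. In SAP 3.3.8 and the Table 12 footnote, tie susceptible to the M100 susceptible category promised in protocol 8.2.2, state its numeric value and the edition used, and reconcile it with the categories in protocol 2.2. If the result departs from the protocol, say so in SAP section 15.
2. Split Table 12 by MIC band for each gyrA result: below 0.125, 0.125 to below 0.5, 0.5 to below 1, and 1 or more.
3. Report PPV and sensitivity also with susceptible taken as below 0.125 and as below 0.5.
4. Keep MIC below 1 as a labelled sensitivity analysis, unless it is shown to be the M100 susceptible category, in which case cite it as such.

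The cost is SAP wording and one wider table. No new data are needed, because protocol 8.2.2 already has every positive culture tested by agar dilution. The downside for the sponsor is a possibly lower reported PPV.

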4. INVESTIGATIONAL PLAN

4.1. Overall Study Design and Plan

This study is a multi-center, single-arm, open-label clinical study to assess the efficacy of one dose of ciprofloxacin given orally in subjects infected with untreated *gyrA* serine 91 genotype *N. gonorrhoeae* as determined by a real-time PCR assay. The study plans to enroll approximately 381 subjects to obtain a per protocol eligible target of 257 subjects age 18 years or older regardless of gender identification who are seeking care in STD clinics at participating sites in the United States. Subjects who have untreated *gyrA* serine 91 genotype *N. gonorrhoeae* of the rectum, or male or female urogenital tract identified by a positive culture or NAAT conducted at a prior visit are offered enrollment in the study. Subjects not consenting to participate in the study receive treatment per local standard of care.

At enrollment, Visit 1 (Day 1), a brief physical exam and medical and sexual history is performed. Subjects have samples collected for *N. gonorrhoeae* culture and *N. gonorrhoeae* NAAT (to include *gyrA* serine 91 genotype) from each infected anatomic site (throat, rectum, male or female urogenital tract) to verify infection status.

Subjects with *gyrA* serine 91 genotype rectal or urogenital *N. gonorrhoeae* receive one dose of directly observed ciprofloxacin 500 mg. Subjects are observed in the clinic for at least 5 minutes after receiving ciprofloxacin and are instructed to return to the clinic or to contact the study site coordinator immediately if they vomit within 1 hour of receiving ciprofloxacin. Subjects who vomit within 1 hour of study drug administration should be retreated for *N. gonorrhoeae* infection with an alternative recommended regimen per local standard of care.

Subjects return for clinical and laboratory assessments at Visit 2 (Day 5-10), the Test of Cure visit. Subjects have repeat samples collected for *N. gonorrhoeae* culture and *N. gonorrhoeae* NAAT from all anatomic sites swabbed at Visit 1 (Day 1).

For Visit 3 (Day 11-14), test results are provided to subjects by phone call. No further follow-up is required for subjects who test culture negative and NAAT negative. Subjects who test culture positive or NAAT positive are referred for standard of care treatment for *N. gonorrhoeae*.

The duration of the study for each subject is approximately 11-14 days. [Table 1](#) provides the study schematic. [Table 2](#) presents the schedule of events for each visit.

The study is monitored for futility. The number of treatment failures among subjects eligible for the Per Protocol (PP) analysis population is monitored by a statistician independent from the study team. If, at any point in the trial, 30 subjects eligible for the PP analysis population are classified as treatment failures, then the statistician will notify DMID to consider termination of the trial.

